Given the rapidly developing nature of the COVID pandemic and the short timeline for submitting the initial NIH grant proposal, we have subsequently made some changes to the design of the study that will improve the quality and rigor of the science and allow for more robust comparisons. The NIH allows for changes in design that improve the quality and rigor of the science. Notably, we have added a control group (n=15) that will receive a tablet with standard guidelines for exercise following COVID-19 infection and hospitalization, the Platform (for testing only) and a Fitbit activity monitor, but not any formal tele-rehabilitation. To collect safety data and encourage retention, a research assistant will contact control participants 1x/week over the course of the intervention (12 weeks). The intervention group (n=30) will receive care as described herein. Therefore, the total projected sample size for this study will be 45 participants. Including a formal control group in addition to the intervention group will allow for more robust evaluation of the value of tele-rehabilitation sessions combined with biobehavioral interventions. We will still be able to compare both the intervention and control groups described to a no-treatment sample that is followed as part of COMIRB 20-0703. We therefore believe the proposed changes are justified to improve the quality of the science and the comparisons/conclusions we will be able to make from these data.

Research Design and Methods

For this rehabilitation pilot, individuals from a separate hospital follow-up study (COMIRB 20-0703) who are 35 years of age and older and speak English will be randomly approached regarding potential participation. Participants will also be recruited through treatment relationships with [name], [name], and [name] (Co-Investigators). Participants will also be recruited via HIPAA A and COMIRB approved flyers in Colorado. Individuals who consent to participate will be randomly allocated to the intervention or control group in a 2:1 ratio; randomization will be stratified based on age (<55 and ≥55), length of mechanical ventilation (<5 days, ≥ 5 days), and gender. The **App-Facilitated Tele-Rehabilitation (AFTER)** program involves tele-rehabilitation delivered in individual formats with biobehavioral interventions to augment adherence and recovery. Outcome assessors will be blinded to group allocation within the AFTER program.

A. Outcome Measure(s):

Data Collection and Outcomes.

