Initial efficacy for change in physical function will be measured by the 30" Chair Stand Test (Hypothesis B primary outcome). The 30" Chair Stand Test requires only a standard height chair (approximately 45cm) and can be visualized on video. The test requires the participant to stand up and sit down as many times as possible in 30 seconds. To facilitate accuracy of the test over video, the participant will be instructed to count out loud during the test each time he/she stands. Further, the test will also be facilitated by the Platform. The 30" Chair Stand Test is responsive to change. Initial efficacy for behavior change will be assessed by Average Daily Step Count, PROMIS Short Form (SF) v1.0 General Self-Efficacy 4a, and PROMIS Short Form (SF) v1.0 Self-Efficacy for Managing Chronic Conditions. Average Daily Step Count (per week)

will be collected via Fitbit. The PROMIS SF v1.0 General Self-Efficacy 4a was developed from the NIH self-efficacy scale, and the short form consists of 4 items rated on a 5-point Likert scale [I am not at all confident (1) to I am very confident (5)].⁸⁴ The PROMIS SF v1.0 Self-Efficacy for Managing Chronic Conditions will also be collected since items on this scale are more specific to managing symptoms during various tasks. The short form is an 8-item scale rated on a 5-point Likert scale which is identical to the General Self-Efficacy scale. It has been validated in individuals with chronic neurological and general medical conditions.⁸⁵ For both PROMIS measures, a higher score is indicative of higher levels of self-efficacy. Additional outcomes for Hypothesis B include 4-stage balance test, Timed Up-and-Go test, MRC dyspnea, and activities-specific balance confidence (ABC) scale to identify and monitor fall risk. The PROMIS Scale v1.2 Global Health will be used to measure quality of life; a higher score is indicative of better quality of life. The 3-Item Loneliness scale will be used to assess loneliness. The Patient Health Questionnaire 8 (PHQ8) will be used to measure depression; a higher score indicates increased severity of depressive symptoms. All the aforementioned outcomes will be collected in both groups.

The following is specific to data collected through the Platform:

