
Confidentiality, privacy, protection of data:

Risks will be minimized by not including personal identifying information on the forms, when possible, and by conducting interviews, functional assessments, and collection of personal information in a secure telehealth platform. All data will be collected using unique patient identification codes. All evaluation forms, reports, and other records will be identified by a coded number to maintain participant confidentiality. All records will be stored in a locked file cabinet. Study data will be collected and managed using REDCap (Research Electronic Data Capture). Clinical information will not be released without written permission of the participant, except as necessary for monitoring by the IRB or NIH. Finally, subjects will be monitored for evidence of distress associated with study completion. Any subjects who express a desire for additional support will be referred to mental health services by [name] via established clinical referral pathways.

E. Potential Scientific Problems:

Potential Recruitment Difficulties: Due to uncertainty surrounding the COVID-19 pandemic, there may be difficulty recruiting 45 participants for the study. For September 22-23, 2020, the current census of COVID-19 positive patients in UHealth hospital was 23 of which 2 were new admits in the past 24 hours. In the same time period, there were a total of 27 admitted patients (1 new in past 24 hours) who tested positive for COVID-19 in hospitals affiliated with the University of Colorado.

Missing Data: All participants with outcome measurements will be included in analysis. The importance of reassessment for data collection will be stressed during enrollment and consent and repeated during study participation. Participants will be contacted repeatedly if they miss reassessment time points, and all efforts will be made to collect data.

Technical Issues: Technical issues are a concern for telerehabilitation and telehealth programs. As such, we have a detailed approach to address any technical issues which may arise.

1. Participants may call the Research PT (or designee) anytime, during regular business hours, with issues or concerns.
2. If a technical issue should arise that the Research PT cannot address, they will contact Blue Marble's Research Associate, [name], to discuss.
3. If needed, [name] will speak directly with the participant to solve the issue.

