4. Although unlikely, Blue Marble's programmer may need to participate on the call to resolve the issue. The programmer has human subjects training.
5. The Research PT (or designee) will keep track of any and all technical issues as this is a feasibility outcome of the study.

F. Data Analysis Plan:

Sample Size: We estimate the proportion of participants at any session with technical difficulties (anticipate $\leq 20\%$), use the platform between sessions (anticipate $\geq 50\%$), and adhere to the intervention (anticipate $\geq 50\%$). Assuming these rates, a sample size of 30 and a two-sided 95% CI, provides a margin of error of 15% for technical difficulties and 18%, for platform use and adherence. We use preliminary 5-time chair rise data to estimate our effect size ($SD=8.7$) in our outcome and assume adjustment variables, including baseline measures, will explain at least 50% of the total variance (R^2). Using linear regression, we anticipate the width of our 95% confidence interval for the group coefficient to be $\pm 0.90 \times 1$ SD at week 6. We anticipate additional precision by using all longitudinal outcome data. We will also provide descriptive statistics for the change from baseline over time, for each group.

We hypothesize (B) tele-rehabilitation is associated with improved physical function in participants previously admitted to the hospital, as measured by change in the 30" Chair Stand Test at 12 weeks. Randomization will be stratified by age (<55 , ≥ 55), sex, and length of mechanical ventilation (< 5 days, ≥ 5 days). Hypothesis A: Descriptive statistics will assess feasibility (i.e., adherence, SUS score, and safety). Hypothesis B will be analyzed with group assignment (AFTER program versus control) as the primary explanatory variable; secondary analyses will be made to COMIRB 20-0703 cohort. Analyses will utilize R (<https://www.R-project.org>), SAS (Cary, NC), and GraphPad Prism (San Diego, CA). Code will be portable and reproducible with documenting libraries and raw data location, as well as code documenting cleaning.

G. Summarize Knowledge to be Gained:

The proposed study will 1) address a great and urgent need to identify predictors of multisystem recovery and long-term health in survivors of COVID-19 and 2) evaluate rehabilitative care to these individuals even, and especially, when they face post-hospitalization barriers to in-person care.

H. References:

References

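### The ±0.90 SD precision stated for the week-6 group comparison is twice what the plan's own inputs give: the half-width is about ±0.45 SD, and 0.90 SD is the full width

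*Combined protocol and SAP*

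**What the plan says.** The precision statement is in section F, Data Analysis Plan, under Sample Size. Adjustment variables, including baseline measures, "will explain at least 50% of the total variance". On that basis, for a linear regression, "we anticipate the width of our 95% confidence interval for the group coefficient to be" ±0.90 × 1 SD at week 6.

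The group sizes are in the paragraph on design changes just before the heading Research Design and Methods: "The intervention group (n=30) will receive care as described herein", and the added control group has n = 15. Allocation is 2:1 and the total is 45.

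Earlier in the Sample Size paragraph, the plan says of the feasibility proportions that a sample of 30 "provides a margin of error of 15% for technical difficulties and 18%, for platform use and adherence".

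The paragraph also reports an SD of 8.7 with this source: "We use preliminary 5-time chair rise data to estimate our effect size". Under Missing Data in section E the plan says "All participants with outcome measurements will be included in analysis", and it gives no expected loss rate.

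**The concern.** The sentence names a width but puts a ± sign in front of the number, and ± denotes a half-width. The two readings differ by a factor of 2, and only one of them fits the design.

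No power calculation or target difference is given for Hypothesis B, so this figure is the whole quantitative case for 30 against 15 on efficacy. Taken literally, it tells a reader that the 95% interval will exclude zero only if the observed adjusted difference is larger than 0.90 SD. Anyone who used it to interpret this pilot, or to plan a later trial, would start from an interval twice as wide as the design implies.

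**Working it through.** **Inputs.** n₁ = 30 and n₂ = 15 (design-changes paragraph). R² = 0.50, linear regression, 95% interval, week 6 (section F, Sample Size). The loss rate is not stated, so it is taken as 0% first and varied below. The SD cancels because the result is in SD units.

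**Formula.** SE = √[(1 − R²)(1/n₁ + 1/n₂)] SD; half-width = critical value × SE.

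**The plan's design**

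- 1/30 + 1/15 = 0.10, so SE = √(0.5 × 0.10) = √0.05 = 0.2236 SD.
- z: 1.96 × 0.2236 = ±0.438 SD; full width 0.877 SD.
- t on 43 df: 2.017 × 0.2236 = ±0.451 SD; full width 0.902 SD.
- t on 39 df (four covariates): 2.023 × 0.2236 = ±0.452 SD; full width 0.905 SD.

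The number 0.90 is reproduced as a full width. As a ± figure it is too large by 0.90/0.451 = 2.0.

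**The other precision figures in the paragraph (n = 30)**

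- Technical difficulties at 20%: 1.96 × √(0.2 × 0.8/30) = 14.3%, against a stated 15%.
- Platform use and adherence at 50%: 1.96 × √(0.5 × 0.5/30) = 17.9%, against a stated 18%.
- Full widths would be 28.6% and 35.8%, so both stated figures are half-widths.

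**Could unstated allowances give ±0.90?** The loss rates here are assumptions.

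| Analysed | R² | 95% half-width (t) |
|---|---|---|
| 30 vs 15 | 0.50 | ±0.45 SD |
| 27 vs 13 (10% loss) | 0.50 | ±0.48 SD |
| 24 vs 12 (20% loss) | 0.50 | ±0.51 SD |
| 30 vs 15 | 0 | ±0.64 SD |
| 24 vs 12 (20% loss) | 0 | ±0.72 SD |

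None reaches ±0.90 SD. At R² = 0.50 it would take a variance inflation of (0.90/0.451)² ≈ 4. Failing that, only 12 to 15 participants in total could be analysed: at 2:1, 12 gives ±0.965 SD and 15 gives ±0.837 SD.

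**Possible origins.** Two slips give the same number. One is a ± sign placed on the full width. The other is dividing the variance by (1 − R²) instead of multiplying: √(0.10/0.5) × 2.017 = 0.902. At R² = 0.50 these cannot be told apart, because √(0.10/0.5) = 0.447 is exactly twice 0.2236. The documents do not settle which occurred, if either, and neither makes ±0.90 correct.

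**The case against.** The strongest reply is that the number is right for the quantity the sentence names. It says width, the full width is 0.902 SD, and the feasibility figures are labelled differently, as margins of error. On this view the defect is a stray sign and not a wrong calculation. This has force as to cause, and a calculation error is not shown. But it concedes that the ± is wrong, which is the correction needed. A reader who has just met two half-widths may well take a ± figure as a third.

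The second reply is that little depends on it. This is a feasibility pilot, no power claim or success threshold for Hypothesis B uses the figure, the error understates precision, and the plan expects further gains from using all longitudinal data. All of that stands, and it limits the consequence to misreading. It does not make the figure correct.

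Two smaller points are also fair. The loss and R² = 0 scenarios are optional context, since the plan states no loss rate and assumes R² of at least 0.50. The origin of the SD of 8.7 does not bear on the result, because it cancels and the plan already names its source.

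**Conclusion.** The concern holds. From the plan's own inputs the week-6 95% interval for the group coefficient is about ±0.45 SD, with a full width of about 0.90 SD. The printed ±0.90 SD is twice the half-width.

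This assumes that all 45 participants are analysed, R² = 0.50, and no material imbalance of covariates between groups. Because the plan assumes R² of at least 0.50, ±0.45 SD is close to the widest interval under its assumptions at full n. With assumed losses of 10% to 20% it becomes ±0.48 to ±0.51 SD.

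The error is in the conservative direction and leaves the sample size, endpoint, model and decision rules untouched. It should still be corrected, because it is the only precision figure for the efficacy comparison.

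**What to change.** Check the calculation, then replace the sentence with something like: *With 30 and 15 participants analysed and R² = 0.50, the anticipated 95% CI half-width for the group coefficient at week 6 is about ±0.45 SD (full width about 0.90 SD).*

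Optionally add the sensitivity: about ±0.51 SD if 20% are lost (an assumed rate), and about ±0.64 SD at full n if covariates explain nothing.

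Also optionally, make clear that 8.7 is the SD of the 5-time chair rise data. The paragraph presents it as the SD of the outcome, whereas the primary outcome is a count: "The test requires the participant to stand up and sit down as many times as possible in 30 seconds". It should not be used to convert the interval into stands.

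The cost is the wording of one or two sentences, with no change to design or analysis.
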